## Memorial Sloan-Kettering Cancer Center IRB Protocol

**IRB#: 08-155A(8)**

will notify the POA of the patient's gynecologic oncologist and the clinic nurse taking patient calls for that gynecologic oncologist that day. No specific responses to these emails will be required, but any actions taken in response to these alerts by clinicians will be tracked (ie, telephone calls, supportive medication prescriptions, new appointments made, etc) using a form emailed to the nurse after the automated email alert (Appendix 5) and the "Ambulatory Care Phone/Email Communication Form" in the EMR. The forms will be collected by the research fellow or by the designated RSA.

It will be emphasized to patients that there is no regular monitoring of information entered into WEBCORE, and that they should call their physician's office if they feel that they require medical attention. This will be emphasized to patients in the informed Consent, during a WEBCORE training session, and on the WEBCORE website. In addition, anytime a patient enters a potentially concerning response into WEBCORE, a popup box will appear on the screen reminding her to consider calling her physician.

If 80% of enrolled patients with home Internet access login to WEBCORE at least four times during the study period we will consider WEBCORE a strategy warranting larger scale evaluation. Patient assessment of the usefulness of WEBCORE will be measured via an exit survey. Clinician perceptions of the potential value of WEBCORE will be evaluated via an email survey and questions asked at a team meeting. Reasons for patient non-compliance will be assessed via results of the backup telephone calls to those who failed to login, and with the exit survey.

Potential benefits of this use of the WEBCORE platform in this context will be assessed by measuring the number and type of clinical interventions made in response to WEBCORE alerts, and by analyzing patient use of WEBCORE in relation to dates of surgery and development of documented post-surgical complications.

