## Memorial Sloan-Kettering Cancer Center IRB Protocol

**IRB#: 08-155A(8)**

We will consider the results of this feasibility study to suggest that WEBCORE is a strategy warranting larger scale evaluation if approximately 80% of enrolled patients login to WEBCORE at least four times from the time of enrollment until six weeks following surgery. Patient assessment of the usefulness of WEBCORE will be measured via an exit survey. Clinician perceptions of the potential value of WEBCORE will be evaluated via an email survey and questions asked at a team meeting. Reasons for patient non-compliance will be assessed via results of the backup telephone calls to those who failed to login, and with the exit survey.

Potential benefits of this use of the WEBCORE platform in this context will be assessed by measuring the number and type of clinical interventions made in response to WEBCORE alerts, and by analyzing patient use of WEBCORE in relation to dates of surgery and development of documented post-surgical complications.

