## Memorial Sloan-Kettering Cancer Center IRB Protocol

**IRB#: 08-155A(8)**

### **4.2.3 Logging into WEBCORE**

Subjects are expected to login to WEBCORE once weekly from a home computer to fill out the online questionnaire. Subjects will be able to login to WEBCORE from any Internet-accessible computer whenever they wish to record symptoms, even if it is more frequently than the recommended weekly interval. Patients will be sent email reminders on the day they are due to login to WEBCORE which are identical to the email reminders currently in use in 04-020 (Appendix 10), and a follow-up email reminder email will be sent when they are overdue to login. Those who fail to respond to the follow-up email will receive a backup telephone call to administer the questionnaire and assess reasons for non-compliance.

Each time a patient logs in to the WEBCORE website, he or she will respond to items in the questionnaire, and these responses will be securely stored in the MSKCC Clinical Research Database (CRDB).

Technical assistance accessing the system will be available 24 hours. Patients will not be offered any financial incentives to login.

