## **9.0 PRIMARY AND SECONDARY OUTCOMES**

### **9.1 Primary Outcome**

The primary objective of this study is to evaluate the feasibility of patients using WEBCORE to track their own symptoms and HRQL while recovering from laparotomy for presumed or confirmed gynecologic cancer. In this pilot feasibility study, we will measure several parameters related to patients' utilization of the WEBCORE system, in order to evaluate the potential for implementation of collecting patient self-reported measures in a gynecologic oncology practice and/or in clinical trials.

- To gauge patients' willingness to record their experiences we will record the ratio of the number of patients approached for study participation to the number who enroll. The proportion of patients approached versus consented will be tracked continuously by the Research Fellow and the designated Surgery RSA.
- We will evaluate the extent to which patients who enroll in the protocol use the WEBCORE system to self-report symptoms and HRQL. Specifically, we will measure how often each user accesses the WEBCORE system, and will note the time and date that utilization occurs. Perfect compliance would be logging on and completing all the questions seven times: once pre-operatively, and then weekly for six weeks following surgery. In keeping with standards for the assessment of feasibility of online platforms, as a crude measure of feasibility, we will consider the study results to suggest that WEBCORE is a strategy warranting larger scale evaluation if approximately 80% of participants login to WEBCORE at least four times during the study period [13]. In our analysis, we will look at WEBCORE utilization (1) over time and (2) in relation to the presence or absence of documented minor and major surgical complications. The proportion of users who logged in with or without a follow-up reminder email will be tabulated. We will assess for attrition of compliance over time by measuring the proportion of patients who login during each consecutive week of observation.
- Results of backup telephone calls made when patients have not logged in will be tabulated to assess if the reported symptoms of such patients differ from reports of patients who have logged in on time, and reasons for non-compliance.

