**11.0 BIOSTATISTICS**

**11.1 Sample Size and Accrual**

The sample size of 110 patients is based on the personnel resources (one dedicated clinical fellow) and time available (approximately one year) to conduct this study. A responder is defined as a patient who logs in and completes at least half of the questionnaire at least 4/7 potential logins. The hypotheses being tested are: 80% is considered acceptable whereas 65% is considered too low. The study requires 79 patients to show a difference from 65% to 80% in percent responders with 90% power and type I error of 4%. If at the end of the study 58/79 are responders then the study will conclude that the use of WEBCORE in this population is feasible.

[figure not shown]

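### Two pass marks lead to the same feasibility conclusion: 80% logging in four times (Sections 1.3, 4.1, 9.1) and 58/79 = 73.4% responders (Section 11). The second misses its stated 4% type I error.

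*Combined protocol and SAP*

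**What the plan says.** Three sections set the mark at or near 80% and count logins only.

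- Section 1.3: "If 80% of enrolled patients with home Internet access login to WEBCORE at least four times during the study period", WEBCORE is judged worth evaluating on a larger scale.
- Section 4.1: the same conclusion "if approximately 80% of enrolled patients login to WEBCORE at least four times".
- Section 9.1 (Primary Outcome): the same conclusion "if approximately 80% of participants login to WEBCORE at least four times during the study period", introduced "as a crude measure of feasibility".

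Section 11 sets out a one-sample test on responders. A responder is a patient who logs in and "completes at least half of the questionnaire at least 4/7 potential logins". Section 11.1 gives the hypotheses as "80% is considered acceptable whereas 65% is considered too low" and says the study needs "79 patients to show a difference from 65% to 80% in percent responders with 90% power and type I error of 4" percent. Feasibility is concluded if 58/79 are responders. Section 11.2 repeats that cut-off and attaches the same consequence as Section 9.1, larger-scale evaluation, with the same citation.

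On logins, Section 4.2.3 lets patients use the system "whenever they wish to record symptoms, even if it is more frequently than the recommended weekly interval". On numbers, Section 11.1 gives 79 as the requirement and 110 as the sample size, and keeps accrual open until at least 80 evaluable patients are enrolled. Section 10 excludes from the feasibility assessment anyone who does not have the planned surgery.

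**The concern.** The plan gives two decision rules for one conclusion and does not rank them. They differ in threshold (about 80% against 73.4%) and in what is counted (four logins at any time against four of seven potential logins, each at least half completed). Section 4.2.3 allows unscheduled logins, and items may be skipped, so a patient can meet the first definition without meeting the second.

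The observed result may well fall between the two thresholds, because that is where results are expected if the true rate is near 75% to 80%. Whether the study is called feasible would then depend on which section is cited, and that choice could be made after the data are seen. The word approximately in Sections 4.1 and 9.1 has no stated width, and Section 1.3 omits it.

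Adopting Section 11 unchanged does not fully resolve the matter, because its cut-off does not deliver the error rates quoted beside it.

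**Working it through.** **Inputs.** From Section 11.1: n = 79, null rate p0 = 0.65, alternative rate p1 = 0.80, cut-off 58, stated type I error 4% and power 90%. From Sections 1.3, 4.1 and 9.1: pass mark 80% or approximately 80%. The pass rule is one-sided. X denotes the number of patients counted as successes, with X ~ Bin(79, p).

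**1. The plan's own figures.** For a rule that passes at X ≥ r, type I error = P(X ≥ r | p = 0.65) and power = P(X ≥ r | p = 0.80).

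| Cut-off | Observed proportion | Type I error | Power |
|---|---|---|---|
| 58 or more | 58/79 = 73.4% | 7.13% | 94.1% |
| 59 or more | 59/79 = 74.7% | 4.33% | 90.4% |
| 60 or more | 60/79 = 75.9% | 2.48% | 85.1% |

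The stated 4% and 90% are not reproduced at 58. A normal approximation does not recover 4% either. With mean 79 × 0.65 = 51.35 and SD √(79 × 0.65 × 0.35) = 4.239, it gives z = (58 − 51.35)/4.239 = 1.57, an error of 5.8%. With a continuity correction, z = (57.5 − 51.35)/4.239 = 1.45 and the error is 7.3%. At 59 the exact figures round to those stated. So n = 79 is sound, and 58 looks like the largest failing count written as the passing count.

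**2. Where the two rules disagree if they count the same event.** 63/79 = 79.7% is below 80% and 64/79 = 81.0% is above it. Section 11 therefore passes and a literal 80% fails for X = 58 to 63. If 63/79 is accepted as approximately 80%, the band is 58 to 62.

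| True rate | P(58 ≤ X ≤ 63) | P(58 ≤ X ≤ 62) |
|---|---|---|
| 80% | 46.4% | 35.3% |
| 75% | 54.8% | 48.0% |

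**3. If an observed 80% governed.** Power at a true 80% would be P(X ≥ 64) = 47.8%, or P(X ≥ 63) = 58.9% if 79.7% is accepted. Neither is near the 90% the sample size was chosen for.

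**4. If the events differ.** Let L ~ Bin(79, 0.80) be the number with four logins and, given L, let R ~ Bin(L, c) be the number who also meet the responder definition. The documents give no value for c, so the values below are assumptions.

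| c (assumed) | Section 11 passes, literal 80% fails: P(R ≥ 58, L ≤ 63) | Section 11 fails, literal 80% passes: P(R < 58, L ≥ 64) |
|---|---|---|
| 100% | 46.4% | 0 |
| 99% | 43.9% | below 0.01% |
| 95% | 28.1% | 0.7% |
| 90% | 8.4% | 11.6% |

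**5. Other analysis sizes.** With 80 evaluable patients, 60 or more gives 3.7% and 89.3%. With 110, 81 or more gives 3.4% and 95.9%. The cut-off for 79 therefore does not carry over unchanged.

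**The case against.** The strongest reply is that a statistician would apply Section 11 without hesitation. It is the biostatistics section, it gives a count and a definition, and it assigns 80% a clear role as the acceptable rate tested against 65%. Section 9.1 itself calls its mark crude and approximate. On that view what remains is loose wording. This is the natural reading, and it is why the fix adopts Section 11. But no sentence states it, Section 1.3 has neither qualifier, and Section 11.2 attaches the same conclusion to the lower mark.

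A second reply is that the 58 to 63 band treats 79.7% as a failure. That is fair for the two sections that say approximately. The narrower band still holds 35% of results at a true 80% and 48% at a true 75%.

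A third is that the two events will rarely differ. Section 9.1 describes perfect compliance as seven completed logins, so four plausibly means four of those seven, and Section 11.5 expects only about 1% of items to be skipped. This has force: at c = 99% the reverse disagreement is negligible, and the 11.6% figure depends wholly on an assumed 90%. The 1% refers to individual items, however, and says nothing about unscheduled logins.

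Finally, 58/79 carries no inequality sign, and read as more than 58 the design nearly meets its stated errors. That is probably what was intended, but as written a result of exactly 58 passes.

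It is also true that this is a single-arm pilot and that the observed proportion can be reported whichever rule is used. The plan nevertheless frames a hypothesis test with error rates and a pass/fail conclusion.

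**Conclusion.** The concern holds and should be fixed. The plan gives two thresholds for its headline conclusion without ranking them. If they count the same event, they conflict over a band with probability 46% (true rate 80%) or 55% (75%) against a literal 80%, and 35% or 48% if 63/79 is accepted as approximately 80%. These figures assume 79 analysed patients and independent binomial outcomes. If the events differ, the rules can also disagree in the other direction, by an amount that depends on a completion rate the documents do not give.

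Separately, the Section 11 cut-off as written has a type I error of 7.1%, not 4%, and power of 94.1%, not 90%. The sample size of 79 is not at fault. The cut-off is one too low for the stated errors, and even 59 gives 4.3%, which meets 4% only after rounding.

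**What to change.** - Make the Section 11 rule and its responder definition the single decision rule, worded identically in Sections 1.3, 4.1, 9.1, 11.1 and 11.2.
- State that 80% is the alternative rate used for power, not the observed pass mark. Keep the percentage with at least four logins as a descriptive measure.
- Write the cut-off with an inequality. Either use 59 or more of 79, with type I error 4.3% and power 90.4%, or keep 58 or more and restate them as 7.1% and 94.1%.
- Apply the rule to enrolled patients who had surgery, in line with Section 10, and say how later withdrawals and removals are counted. The responders-to-enrollees and responders-to-eligible ratios in Section 11.2 can stay descriptive.
- If the number analysed is not 79, set the cut-off by an exact binomial test against 65% and report the resulting errors. For example, 60 or more of 80 gives 3.7% and 89.3% (just under 90% power), and 81 or more of 110 gives 3.4% and 95.9%.

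The cost is wording in five sections and either one count changed by one or two error rates restated. No extra patients or data are needed.

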**IRB#: 08-155A(8)**

**9.2 Secondary Outcomes**

**9.2.1 Patient Assessment of WEBCORE**

Patient assessment of the usefulness of WEBCORE will be measured via an exit questionnaire (Appendix 2).

**9.2.2 Clinician Assessment of WEBCORE**

At the completion of the study period, an email clinician survey will be administered (Appendix 8), and a focus group will be scheduled with all clinicians and support personnel involved in the care of enrolled patients (physicians, nurses, Session Assistants). Specific open-ended questions will be asked verbally to assess qualitative impressions of WEBCORE, and to obtain suggestions for future development of WEBCORE (Appendix 6). Questions will include whether WEBCORE was felt to be useful overall, not useful, or detrimental; whether it saved or consumed time; whether summary reports should be used to replace other assessment documents in the patient chart; and whether clinicians feel that patient self-generated reports accurately depict levels of toxicity.

**9.2.3 Clinician Responses to Alerts**

Each time an automated email alert is sent to the primary clinical team (nurse), the clinician will be emailed a form to assess the response to the alert (Appendix 5), which the clinical fellow coordinating the study will collect. If the nurse indicates that a patient was contacted as a result of the automated email, the research fellow or RSA will look at the “Ambulatory Care Phone/Email Communication Form” in the EMR and record what action was taken. Possible responses include: diagnostic test, prescription, office visit scheduled, UCC visit recommended, no action, other.

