A WEBCORE report summarizing patient symptom trends will be printed and made available to the clinician at the time of the post-operative visit. Additionally, if a patient submits a response that is concerning according to pre-specified limits set by the gynecologic oncology service, an automated email alert flagged as “urgent” and titled “severe Patient-reported symptom” will be sent in real-time to the research fellow, the designated RSA and the PI of the study. The research fellow will forward the email to the POA of the patient’s gynecologic oncologist and to the clinic nurse taking patient calls for that gynecologic oncologist that day. (This is the same system used presently to triage patient phone calls.) If the research fellow is not available, coverage will be provided by the designated RSA. In that event, the designated RSA will notify the POA of the patient’s gynecologic oncologist and the clinic nurse taking patient calls for that gynecologic oncologist that day. No specific responses to these emails will be required, but any actions taken in response to these alerts by clinicians will be tracked (ie, telephone calls, supportive medication prescriptions, new appointments made, etc) using a form emailed to the nurse after the automated email alert (Appendix 5) and the “Ambulatory Care Phone/Email Communication Form” in the EMR. The forms will be collected by the research fellow or by the designated RSA.

It will be emphasized to patients that there is no regular monitoring of information entered into WEBCORE. In addition, anytime a patient enters a potentially concerning response into WEBCORE, a popup box will appear on the screen reminding her to consider calling her physician.

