## Memorial Sloan-Kettering Cancer Center IRB Protocol

**IRB#: 08-155A(8)**

that triggered the alert. The form will take approximately 5 minutes to fill out. If the nurse indicates that a patient was contacted as a result of the automated email, the research fellow or RSA will look at the “Ambulatory Care Phone/Email Communication Form” in the EMR and record what action was taken. Forms will be collected by the research fellow or RSA. Possible responses include: diagnostic test, prescription, office visit scheduled, UCC visit recommended, no action, other.

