## **8.0 TOXICITIES/SIDE EFFECTS**

Minimal risk of psychological distress is posed by study questions that ask participants to identify their current problems. However, since study items were chosen to reflect what are likely to be existing concerns, the present study is not expected to markedly increase participants' psychological distress above their routine concerns. WEBCORE allows a participant to skip any question(s) that she chooses, without compromising her ability to complete the rest of the questionnaire. Formal testing of depression is not included as part of the questionnaire, however, if a patient responds “quite a bit” or “very much” to the question, “Did you feel depressed?”, an automatic email alert will be sent to the clinic nurse and the research fellow, who will follow up with the patient. In addition, any patient who communicates distress to the RSA or research fellow verbally will be referred for counseling. In the unlikely event of significant acute distress, participants will be referred to a staff member from the Department of Psychiatry and Behavioral Sciences. If a research participant indicates that s/he is acutely suicidal and poses a significant and acute risk of self-harm, this information will be shared with their attending physician so that timely and appropriate psychiatric assessment and care can be provided by the MSKCC

**Memorial Sloan-Kettering Cancer Center  
IRB Protocol**

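### Sections 7.5.1 and 9.2.3 tie the EMR look-up after an alert to the nurse form reporting contact, so the count of actions in 11.4 may miss some, and unreturned forms have no category of their own

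*Combined protocol and SAP*

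**What the plan says.** Sections 1.3, 4.1, 4.2.5 and 7.5.1 share a general commitment: "any actions taken in response to these alerts by clinicians will be tracked", "using a form emailed to the nurse after the automated email alert (Appendix 5) and the" EMR communication form. No condition is attached to the second source. The same paragraphs add "No specific responses to these emails will be required" and, on the paperwork, "The forms will be collected by the research fellow or by the designated RSA".

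The working step comes at the end of 7.5.1 and again in 9.2.3. In 9.2.3 it reads "If the nurse indicates that a patient was contacted as a result of the automated email, the research fellow or RSA will look at the" EMR communication form, after which the action is recorded. The answer list follows: "Possible responses include: diagnostic test, prescription, office visit scheduled, UCC visit recommended, no action, other".

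The nurse is not the only person who may act. Under 4.1 the alert is forwarded to the surgeon's POA as well as to the nurse covering calls. Under 14.1 it reaches the nurse and/or physician, the fellow and the RSA. For a depression response, section 8.0 says "an automatic email alert will be sent to the clinic nurse and the research fellow, who will follow up with the patient".

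Section 11.4 tabulates the phone calls and actions that followed alerts. It names no denominator and describes the result as descriptive and hypothesis-generating.

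**The concern.** The general statement promises complete ascertainment from two sources. The procedure makes the second source depend on a positive answer in the first. A record that could show what happened when the form is missing or incomplete is not opened in those cases.

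The affected outcome belongs to Secondary Aim 2, which names nurse–patient calls and resulting interventions. Sections 1.3 and 4.1 use the number and type of interventions after alerts to assess potential benefit. Section 11.4 looks to the tally for signs that alerts led to important contacts, as a reason for further study. A descriptive count is only as good as its ascertainment, because no later model or test repairs it. Losses by this route can only lower the count.

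**Working it through.** The plan states no expected number of alerts, form return rate or action rate for this study, so there is no figure to reproduce. The check is mainly a reading of the procedure case by case.

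**Step 1. What the procedure in 7.5.1 and 9.2.3 captures**

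| Situation after an alert | EMR form read? | Result |
|---|---|---|
| Form returned, contact reported | Yes | Action recorded |
| Form returned, no contact reported, but someone acted | No step provided | Action not captured |
| Form not returned | No step provided | Action not captured; no category for the alert |
| Form returned, patient made the call herself | No step provided | Arguably right for a count of actions caused by the email, but the call is not shown |

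**Step 2. Whether another section closes the gap**

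- Section 11.4 counts calls and actions and has no rule for unreturned forms.
- Section 11.5 covers skipped items on patient questionnaires only.
- Section 13.1 requires routine reports on missing data and inconsistencies. It does not ask for an EMR check per alert and sets no reporting rule for nurse forms.
- The answer list in 9.2.3 includes no action but has no entry for a form not returned.

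**Step 3. How a shortfall would work (illustration only)**

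Inputs: the earlier chemotherapy study in 3.5 had 42 alerts and 7 telephone contacts. I treat each contact as belonging to a separate alert. Let r be the share of forms returned and s the share of contacts the nurse reports. Both are assumptions, and return is taken as unrelated to contact.

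- Contacts recorded = 7 × r × s
- Rate over all alerts, with unreturned forms contributing no contact = 7 × r × s / 42
- Rate with unreturned forms left out = 7 × s / 42

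| r | s | Contacts recorded | Rate over all alerts | Rate, unreturned left out |
|---|---|---|---|---|
| 1.0 | 1.0 | 7.0 | 16.7% | 16.7% |
| 0.9 | 1.0 | 6.3 | 15.0% | 16.7% |
| 0.8 | 1.0 | 5.6 | 13.3% | 16.7% |
| 0.7 | 1.0 | 4.9 | 11.7% | 16.7% |
| 0.5 | 1.0 | 3.5 | 8.3% | 16.7% |
| 1.0 | 0.8 | 5.6 | 13.3% | 13.3% |
| 0.8 | 0.8 | 4.5 | 10.7% | 13.3% |

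The shortfall in the count is 1 − r × s, which simply returns the assumptions. The table shows the mechanism and is not an estimate for this study. It does show two things. The count falls with r however unreturned forms are coded. The rate depends on the coding, which the plan does not specify.

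**The case against.** Several stronger readings are tempting, and the documents do not support them.

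- **That an alert without a form is counted as no action.** No section says so. In 9.2.3 that entry is one of the possible responses, and nothing assigns it to a form that never came back. Such an alert could be chased, treated as missing or left out.
- **That the plan contains two rival rules.** Section 7.5.1 holds both statements and reads naturally as a general statement followed by its procedure. The text also says if, not only if. What stands is that the procedure does not deliver all that the general statement promises.
- **That every action by someone other than the nurse is lost.** The trigger is passive, so a nurse who knows of a physician's or the office's call can report it. The fellow collects the forms and would know of their own follow-up. What stands is that the capture of others' actions depends on the nurse knowing and reporting them.
- **That the undercount can be given as a percentage.** As shown above, any such figure restates an assumed return rate, borrowed onto a chemotherapy population.

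The best argument for the present wording is attribution. Section 11.4 counts calls that the alerts brought about, and the nurse's statement supplies that link. The popup in 4.2.5 asks the same patient to consider calling the office, so an unconditional EMR search could credit her own call to the email. This objection stands, and the fix has to meet it.

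The fellow and RSA also receive the alerts and collect the forms, so they can see which are outstanding. That makes chasing possible but does not require it. The content of Appendix 5 is not in the text available, so how it records who acted cannot be judged.

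**Conclusion.** The point holds as a gap in ascertainment. Followed as written, 7.5.1 and 9.2.3 miss actions after an unreturned form and actions the nurse does not report. Unreturned forms are also not distinguished from replies of no action. The count in 11.4 may be too low. The size cannot be estimated from the documents, and if all forms come back with complete reporting there is no loss.

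The weight is modest. The outcome is secondary and descriptive, with no test or threshold. The primary decision, 58 responders out of 79, does not use it. The change is worth making because it is specific and cheap, and because the general data quality reports in 13.1 do not provide it.

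**What to change.** In 7.5.1 and 9.2.3, have the fellow or RSA read the EMR communication form for every alert, within a period after the alert that is fixed in advance. This should apply whatever the nurse form says and whether or not it came back.

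Tabulate two groups separately:

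- (a) actions that the nurse form or the EMR entry attributes to the alert;
- (b) other actions found in that period, such as calls the patient made herself.

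Keeping (b) apart protects the count of actions caused by alerts from inflation.

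In 11.4, use all alerts sent as the denominator, and report forms returned per alert, with not returned shown separately from no action.

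The cost is a wording change and some extra look-ups by staff who already open the same form for some alerts. At the earlier study's volume this would be about 42 − 7 = 35 additional look-ups, if its seven contacts fell on separate alerts and only those would have been checked anyway. Some uncertainty about attribution will remain, but it will be visible in the split between (a) and (b).
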